| Dispense IP   | X  | X              | X              | X              | X              | X              |                |                |
| IP compliance j                            | X  | X              | X              | X              | X              | X              | X              | X              |
| Dispense SDAL   | X  | X              | X              | X              | X              | X              |                |                |
| Collect, review, and enter data from SDAL             | X  | X              | X              | X              | X              | X              | X              | X              |
| Clinical Efficacy/Health Outcomes                     |  |                |                |                |                |                |                |                |
| MRI of the SIJ dd                          |  |                |                |                |                |                | X z | X k |
| Linear BASMI  |  | X              |                |                | X              |                | X              | X              |
| Chest expansion                                       |  | X              |                |                | X              |                | X              | X              |
| Occiput to wall distance                              |  | X              |                |                | X              |                | X              | X              |
| Enthesitis (MASES and SPARCC)                         |  | X              |                |                | X              |                | X              | X              |
| Assessment of TJC/SJC (46/44)                         |  | X              |                |                | X              |                | X              | X              |
| Healthcare resource utilization                       |  |                | X              |                | X              |                | X              | X              |
| Patient Global Assessment of Disease Activity NRS     | X  | X              | X              | X              | X              | X              | X              | X              |
| Spinal pain   | X  | X              | X              | X              | X              | X              | X              | X              |

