**Illustration of study design for Clinical Protocol I1F-MC-RHBX (footnotes)**

- a All patients will receive 2 injections at baseline at Week 0 to maintain the blind with a 80-mg or 160-mg starting dose of ixekizumab or placebo.
- b Beginning at Week 16 and up to Week 44, any patient, regardless of their original treatment group, may be identified by an investigator based on clinical judgment as an inadequate responder and receive rescue treatment. At such time changes in background therapy (including, but not limited to NSAIDs, nonbiologic DMARDs or the use of rescue biologic treatment) can be made at the discretion of the investigator, while remaining blinded to the original randomization treatment assignment. Changes in ongoing medications at that time can include changes in dose of NSAIDs or nonbiologic DMARDs, including the introduction of new medications. Investigator may also decide to use biologic rescue of ixekizumab 80 mg Q2W with an 80-mg starting dose.
- c Following any treatment modifications, investigators are to reevaluate the clinical status of the patient as appropriate to assess effect of treatment modification. Treatment guidelines recommend a minimum period of 12 weeks to evaluate effect of biologic treatment modifications; however, if in the opinion of the investigator, a patient does not show any clinical improvement after at least 8 weeks of the ixekizumab 80 mg Q2W treatment modification, then the investigator may consider discontinuation of the patient from ixekizumab treatment. Such patients may then receive other medical therapies (potentially including a TNF inhibitor) that are prescribed by their physician and are to remain in the study until Week 52 per study schedule.
- d Patients who have taken at least 1 study dose and who discontinue study treatment prior to Week 16 or study participation (regardless of timing) are to complete an ETV and enter into post-study follow-up for at least 12 weeks after the ETV date or the last regularly scheduled visit. Patients whose ETV or last regularly scheduled visit is longer than 12 weeks after their last investigational study medication dose are not required to enter into the Post-Study Follow-Up Period. V801 and V802 are required for patients in the Post-Study Follow-Up Period; V803 may be needed depending on neutrophil counts.

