## 5.2. Determination of Sample Size

Approximately 300 patients will be randomized at a 1:1:1 ratio in the Blinded Treatment Dosing Period (Period 2) to ixekizumab 80 mg Q2W, ixekizumab 80 mg Q4W, and placebo. With 100 patients per treatment group, this study will have approximately 98% power to test the superiority of ixekizumab Q2W to placebo for the ASAS40 at Week 16. The following assumptions were used for the power calculations for ASAS40 response rates at Week 16 regardless of starting dose: 46% for ixekizumab 80 mg Q2W treatment group and 18% for the placebo group. A 2-sided Fisher's exact test at the 0.05 level is assumed. These assumptions are based on the data from historical clinical studies in nonrad-axSpA patients with objective signs of inflammation (etanercept, adalimumab, certolizumab, and golimumab [Sieper et al. 2013; Dougados et al. 2014; Landewé et al. 2014; Sieper et al. 2015]).

There is little data from similarly designed 52-week placebo-controlled trials regarding the ASAS40 response rate for active and placebo treated patients to guide power estimation at Week 52. [Table RHBX.5.1](#) provides power estimates to test the superiority of ixekizumab Q2W to placebo for the ASAS40 at Week 52, assuming various ASAS40 response rates for ixekizumab Q2W and placebo at Week 52. A 2-sided Fisher's exact test at the 0.05 level is assumed.

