## **6.1.2. General Considerations for Analyses during the Blinded Treatment Dosing Period (Period 2)**

### **6.1.2.1. Intent-to-Treat Population and Safety Population**

Period 2 starts at the first injection of study treatment at Week 0 (Visit 2) and ends on the date of Week 52 (Visit 15) or the early termination visit (ETV; between Weeks 0 and 52). For patients who were deemed as inadequate responders by their investigators and were treated with biologic rescue of ixekizumab 80 mg Q2W, only data up to the time of initiation of biologic rescue of ixekizumab 80 mg Q2W will be included in the Period 2 analyses using the ITT and Safety Populations. These patients will be considered nonresponders to categorical assessment per the nonresponder imputation (NRI) method after initiation of biologic rescue with ixekizumab 80 mg Q2W. Data collected after biologic rescue therapy has started will be summarized separately for the IR Population (Section 6.1.2.2).

Baseline for ITT and Safety Populations will be defined as the last available value before the first injection for efficacy, health outcomes, and safety analyses. In most cases, this will be the measure recorded at Week 0 (Visit 2). For efficacy measures, if the patient does not take any injection, the last available value on or prior to randomization date will be used. Change from baseline (CFB) will be calculated as the visit value of interest minus the baseline value. For safety analyses using a baseline period, the baseline period is defined as the time from Visit 1 to the date/time of the first injection.

Comparisons between each initially randomized ixekizumab treatment group (80 mg Q2W or 80 mg Q4W) and initially randomized placebo will be performed for all analyses in Period 2.

The randomization to treatment groups is stratified by country and screening MRI/CRP status (positive MRI and elevated CRP; positive MRI and nonelevated CRP; negative MRI and elevated CRP) as described in Protocol Section 6.2. The countries will be categorized into geographic regions for analysis. Geographic regions are defined in Table RHBX.6.3. Unless otherwise specified, the statistical analysis models will adjust for geographic region and screening MRI/CRP status.

Screening MRI and CRP status included in all the analysis models for Period 2 is determined based on the MRI readings and central lab CRP values obtained at screening visit (Visit 1).

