Healthcare Resource Utilization	Healthcare resource utilization data regarding the number of visits to medical care providers, such as general practitioners, specialists, physical, or occupational therapists, and other nonphysical care providers for services outside of the clinical trial; emergency room admissions; hospital admissions; and concomitant medications will be recorded by the investigator in the study's CRF.	Visits to medical care providers (except hospitals)	Derivation will be performed within each treatment period	NA
		Days in hospital		
		Number of hospital admissions (Medical ICU, surgical ICU, coronary ICU, general ward, trauma unit, unknown or other)		
		Healthcare providers (type of specialist for healthcare practitioner)		

Abbreviations: ICU = intensive care unit; NA = not applicable; UK = United Kingdom; VAS = visual analog scale.

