**Table RHBX.6.15. Description of Exploratory Health Outcomes and Quality-of-Life Analyses**

Measure	Variable	Analysis Method (Sections 6.1 and 6.3)	Population (Section 6.1.1)	Comparison / Time Point
European Quality of Life – 5 Dimensions 5 Level (EQ-5D-5L)	EQ-5D mobility, EQ-5D self-care, EQ-5D usual activities, EQ-5D pain/discomfort, EQ-5D anxiety/depression	For each EQ-5D dimension, the proportion of patients with “no problems” will be analyzed by: Logistic regression analysis with NRI; Fisher’s exact test with NRI	ITT Population	IXE80Q2W & IXE80Q4W vs. placebo at Weeks 16 and 52
	Change from baseline in: EQ-5D-5L UK Population-based index score, EQ-5D VAS	ANCOVA with mBOCF	ITT Population	IXE80Q2W & IXE80Q4W vs. placebo at Weeks 16 and 52
Healthcare Resource Utilization	Visits to medical care provider; Days in Hospital; Number of hospital admissions; Healthcare provider	Descriptive statistics	ITT Population	Overall comparison in Period 2 by Kruskal Wallis test

Abbreviations: ANCOVA = analysis of covariance; EQ-5D-5L = European Quality of Life – 5 Dimensions 5 Level; ITT = intent-to-treat; IXE80Q2W = ixekizumab 80 mg every 2 weeks; IXE80Q4W = ixekizumab 80 mg every 4 weeks; mBOCF = modified baseline observation carried forward; NRI = nonresponder imputation; UK = United Kingdom; VAS = visual analog scale.

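### Healthcare use is compared across arms with no adjustment for observation time, although ITT data stop at rescue; this can distort the comparison of provider visits (exploratory, minor).

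*SAP*

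**What the plan says.** SAP Table RHBX.6.15 lists the healthcare-use variables as "Visits to medical care provider; Days in Hospital; Number of hospital admissions; Healthcare provider". They are to be described in the ITT Population, with "Overall comparison in Period 2 by Kruskal Wallis test". The derivation table, RHBX.6.14, adds only "Derivation will be performed within each treatment period". Neither table mentions a rate, an offset or annualisation.

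SAP 6.1.2.1 says that Period 2 "ends on the date of Week 52 (Visit 15) or the early termination visit". For patients given ixekizumab rescue, however, "only data up to the time of initiation of biologic rescue of ixekizumab 80 mg Q2W will be included in the Period 2 analyses" that use the ITT and Safety Populations. The design footnotes set the rescue window: "Beginning at Week 16 and up to Week 44, any patient, regardless of their original treatment group", may be judged an inadequate responder.

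Elsewhere the SAP does allow for unequal time. Section 6.13.2 plans person-time rates for adverse events in the same pre-rescue part of Period 2, and Table RHBX.6.5 plans exposure-adjusted rates with Poisson regression for anterior uveitis.

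**The concern.** A count accumulates with time. If follow-up ends early for rescued patients and the arms differ in rescue, the arms differ in opportunity to record a visit even when the underlying use is the same. A rank test on the totals cannot separate the two.

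Unequal rescue is plausible on the sponsor's own planning figures. Rescue is for inadequate responders, and the sample size assumes Week 16 ASAS40 response of 46% on ixekizumab Q2W against 18% on placebo. Protocol 8.1.3.2 says these data are collected to support economic evaluation, and Table RHBX.6.15 gives the only between-arm test specified for them. The test could signal a difference that is only follow-up time, or miss a real one.

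**Working it through.** **The plan's own figure.** The documents state no figure for healthcare use. The sample size supplies the arm size: "With 100 patients per treatment group", 46% v 18%, two-sided Fisher's exact test at 0.05, power about 98%. Exact enumeration gives 98.8%. The Week 52 entry for 30% v 15% gives 66.9% against the stated 66%. So 100 per arm is used below.

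**Observed time per patient.** Rescue at Week 16 leaves 16/52 = 31% of full follow-up; rescue at Week 44 leaves 44/52 = 85%.

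**Observed time per arm.** Treatment modification is scheduled at Weeks 16, 20, 24, 28, 32, 36 and 44 (Protocol Appendix 2). If rescue is spread evenly over these, the mean rescue week is 200/7 = 28.57. With rescue proportion p, mean observed years = 1 - p x (1 - 28.57/52) = 1 - 0.4505p.
- p = 0.6: 0.730 years
- p = 0.4: 0.820 years
- p = 0.3: 0.865 years

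With equal true use of 4 visits a year and rescue of 60/30/30% (placebo/Q4W/Q2W), expected counts are 4 x 0.730 = 2.92 on placebo and 4 x 0.865 = 3.46 on each ixekizumab arm. Placebo looks 1 - 0.730/0.865 = 16% lower with no true difference.

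**Effect on the test.** Rescue proportions, visit rates, dispersion and rescue timing are all assumptions. Counts are gamma-Poisson and the nominal level is 5%. Rejection rates under equal true use of 4 visits a year:

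| Rescue (placebo/Q4W/Q2W) | A: gamma shape 1, rescue weighted to Weeks 16-24, 3000 trials | B: dispersion 0.5, even rescue times, 1000 trials |
|---|---|---|
| 50/40/40% | 7% | 5% |
| 60/40/40% | 12% | 13% |
| 60/30/30% | 24% | 26% |

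- The Monte Carlo standard error of the 5% entry is about 0.7 points, so it is compatible with 6%.
- Further runs with other rescue timing and dispersion give 9-14% at 60/40/40% and 15-22% at 60/30/30%.
- With strong overdispersion (gamma shape 0.3), 60/40/40% gives only 6-7%.
- With equal rescue of 40% in every arm the rate is about 5%.
- Over 2 to 8 visits a year under B, the ranges are 5-8%, 10-15% and 17-27% for the three rows.

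**Rare events.** At 0.05-0.1 admissions a year and 60/30/30% rescue, the test rejects in about 6%, so there is almost no distortion.

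**Masking.** With true placebo use of 5 a year against 4 and 60/30/30% rescue, truncation cuts the rejection rate from 39% to 6% (mean counts 3.63 v 3.46).

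**Direction.** Suppose rescued patients use r times the care of others in every arm. At 60/30/30% and even rescue times (rescued patients observed 28.57/52 = 0.5495 of a year), mean counts are 4 x (0.4 + 0.6 x 0.5495r) on placebo and 4 x (0.7 + 0.3 x 0.5495r) on ixekizumab. They are equal when 0.3 = 0.1648r, that is r = 1.8. At r = 2 placebo is slightly higher, 4.24 v 4.12.

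**With time in the analysis.** A Poisson model with a log-time offset and robust standard errors recovers about 4.0 per patient-year in every arm and rejects in 3-8% (300 runs per setting, standard error about 1.3 points). Kruskal-Wallis on rates rejects in about 5%.

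**The case against.** Several stronger readings are tempting, and the documents do not support them.

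- **The SAP prescribes raw counts.** It does not say so. This is inferred from the variables listed and the absence of any denominator; nothing contradicts it, but nothing states it.
- **The rescue cut certainly applies.** SAP 6.1.2.1 is broad, but the ITT definition in SAP 6.1.1 and Protocol 9.2.1 confine the cut to the primary Period 2 analyses. Healthcare use is exploratory, so the texts leave room for counting all use to Week 52.
- **Placebo must show fewer contacts.** Truncation lowers the more-rescued arm relative to its own true rate. Whether that arm ends up lowest depends on how much care rescued patients use.
- **Placebo looks cheaper.** The SAP compares use and plans no cost analysis.
- **All the measures are affected.** The effect matters for frequent provider visits, not for rare admissions.

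There is also partial mitigation. SAP 6.10.6.2 reports time to rescue by arm and SAP 6.13.1 reports exposure up to rescue, so unequal observation would be visible to a careful reader.

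A simple offset of pre-rescue time is itself open to challenge. The Protocol Appendix 2 row "Healthcare resource utilization" is marked at Weeks 0, 8, 16, 28, 36, 52 and early termination only. For a rescue at Week 24 the last collection is Week 16, so such an offset could pair 24 weeks of time with 16 weeks of data.

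All of this stands and limits the point. It does not remove the mismatch between the broad rescue cut in 6.1.2.1 and a between-arm test with no time adjustment.

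**Conclusion.** The point holds, at minor severity. Read as written, Table RHBX.6.15 with SAP 6.1.2.1 compares patients whose observed time may differ by a factor of 52/16 = 3.25, using a test that ignores it. If rescue is more frequent on placebo, placebo's recorded provider visits understate its true rate. At 4 visits a year the false-positive rate is near nominal for a 10-point gap in rescue (about 6-7%), 9-14% for a 20-point gap and 15-26% for a 30-point gap. It is less with strong overdispersion and about 5% with equal rescue. A real excess on placebo can be hidden.

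These sizes rest on rescue proportions, contact rates, dispersion and rescue timing that the documents do not give. The analysis is exploratory and outside the multiplicity scheme, so no primary or major secondary conclusion is touched.

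**What to change.** 1. Analyse provider visits, and hospital days and admissions where counts allow, as rates: negative binomial regression with treatment and an offset of log(time covered by the counted data). At minimum, apply Kruskal-Wallis to rates per patient-year.
2. Match the two windows. Either count dated contacts up to rescue, or end both count and time at the last healthcare-use collection (Weeks 8, 16, 28, 36, 52 or early termination) on or before rescue. Treat early discontinuation in the same way.
3. Report observation time by arm, and add Weeks 0-16 counts, where planned follow-up is the same in all arms.
4. State that the rate analysis assumes use before rescue is representative of the patient's use.
5. Reconcile SAP 6.1.1 and 6.1.2.1 on whether the rescue cut applies to this exploratory analysis. If all use to Week 52 is intended regardless of rescue, say so.

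The cost is SAP wording and routine programming. Ending count and time at a collection visit uses only the scheduled collections. The dated-contact option depends on whether the case report form records contact dates, which the documents do not say.

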## 6.19. Annual Report Analyses

Annual report analyses will be documented in a separate document.

## 6.20. Clinical Trial Registry Analyses

Additional analyses will be performed for the purpose of fulfilling the Clinical Trial Registry (CTR) requirements.

Analyses provided for the CTR requirements include summary of AEs, provided as a dataset which will be converted to an XML file. Both Serious Adverse Events and 'Other' Adverse Events are summarized: by treatment group, by MedDRA PT.

- An AE is considered 'Serious' whether or not it is a TEAE.
- An AE is considered in the 'Other' category if it is both a TEAE and is not serious. For each Serious AE and 'Other' AE, for each term and treatment group, the following are provided:
  - the number of participants at risk of an event
  - the number of participants who experienced each event term
  - the number of events experienced.
- Consistent with [www.ClinicalTrials.gov](http://www.ClinicalTrials.gov) requirements, 'Other' AEs that occur in fewer than 5% of patients/subjects in every treatment group may not be included if a 5% threshold is chosen (5% is the minimum threshold).
- Adverse event reporting is consistent with other document disclosures such as the CSR.

## 7. Unblinding Plan

Refer to a separate blinding and unblinding plan.

## 9. Appendices

CCI

The image shows the letters 'CCI' in a large, bold, red, sans-serif font. The letters are positioned in the upper left quadrant of a large black rectangular area that covers most of the page. The 'C's are slightly open at the top, and the 'I' is a simple vertical bar.

CCI

The image shows a large, stylized logo consisting of the letters 'C', 'C', and 'I' in a bright red color. The letters are set against a solid black background. The 'C's are thick and rounded, and the 'I' is a simple vertical bar. The logo is positioned in the upper left quadrant of the page.

The image shows the logo for CCI (Contract Research Organization) in a large, bold, red font. The letters 'C', 'C', and 'I' are stylized and set against a solid black rectangular background that covers most of the page.

The image shows a large, stylized logo consisting of the letters 'C', 'C', and 'I' in a bright red color. The letters are set against a solid black rectangular background that occupies the upper portion of the page. The 'C's are thick and rounded, and the 'I' is a simple vertical bar.

The image shows a large, stylized logo consisting of the letters 'C', 'C', and 'I' in a bright red color. The letters are set against a solid black rectangular background that covers most of the page. The 'C's are thick and rounded, and the 'I' is a simple vertical bar.

The image shows a large, stylized logo consisting of the letters 'C', 'C', and 'I' in a bright red color. The letters are set against a solid black background. The 'C's are thick and rounded, and the 'I' is a simple vertical bar. The logo is positioned in the upper left quadrant of the page.

The image shows a large, stylized logo consisting of the letters 'C', 'C', and 'I' in a bright red color. The letters are set against a solid black background. The 'C's are thick and rounded, and the 'I' is a simple vertical bar. The logo is positioned in the upper left corner of the page.

CCI

The image shows a large, stylized logo consisting of the letters 'C', 'C', and 'I' in a bright red color. The letters are set against a solid black rectangular background that covers most of the page. The 'C's are thick and rounded, and the 'I' is a simple vertical bar.

A large, stylized logo consisting of the letters 'C', 'C', and 'I' in a bright red color. The letters are bold and have a slightly irregular, hand-drawn appearance. They are positioned in the upper left quadrant of a large black rectangular area that covers most of the page.

[figure not shown]
CCI

The image shows the logo for CCI (Centers for Medicare & Medicaid Innovation). The letters 'C', 'C', and 'I' are rendered in a large, bold, red, sans-serif font. The 'C's are stylized with a slight gap at the top and bottom. The 'I' is a simple vertical bar. The logo is positioned in the upper left corner of a large black rectangular area that covers most of the page.

The image shows a large, stylized logo consisting of the letters 'C', 'C', and 'I' in a bright red color. The letters are set against a solid black background. The 'C's are thick and rounded, and the 'I' is a simple vertical bar. The logo is positioned in the upper left quadrant of the page.

[figure not shown]
The image shows a large, stylized logo consisting of the letters 'C', 'C', and 'I' in a bright red color. The letters are set against a solid black rectangular background that covers most of the page. The 'C's are thick and rounded, and the 'I' is a simple vertical bar.

The image shows the logo for CCI (Central Confidentiality Institute) in a large, bold, red font. The letters 'C', 'C', and 'I' are stylized, with the 'I' being a simple vertical bar. The logo is positioned in the upper left corner of a large black rectangular area that covers most of the page.

A large, stylized logo consisting of the letters 'C', 'C', and 'I' in a bright red color. The letters are set against a solid black rectangular background that covers most of the page. The 'C's are thick and rounded, and the 'I' is a simple vertical bar.

[figure not shown]
CCI

A large, stylized logo consisting of the letters 'C', 'C', and 'I' in a bright red color. The letters are set against a solid black rectangular background that covers most of the page. The 'C's are thick and rounded, and the 'I' is a simple vertical bar.

The image shows the logo for CCI (Cognate Clinical Innovations) in a large, bold, red font. The letters 'C', 'C', and 'I' are stylized, with the 'I' being a simple vertical bar. The logo is positioned in the upper left corner of a large black rectangular area that covers most of the page.

A large, stylized watermark consisting of the letters 'C', 'C', and 'I' in a bright red color. The letters are set against a solid black rectangular background that covers most of the page. The 'C's are thick and rounded, and the 'I' is a simple vertical bar.

A large, stylized watermark consisting of the letters 'C', 'C', and 'I' in a bright red color. The letters are set against a solid black rectangular background that covers most of the page. The 'C's are thick and rounded, while the 'I' is a simple vertical bar.

[figure not shown]

CCI

The image shows a large, stylized logo consisting of the letters 'C', 'C', and 'I' in a bright red color. The letters are set against a solid black rectangular background that covers most of the page. The 'C's are thick and rounded, and the 'I' is a simple vertical bar.

The image shows a large, stylized logo consisting of the letters 'C', 'C', and 'I' in a bright red color. The letters are set against a solid black rectangular background that covers most of the page. The 'C's are thick and rounded, and the 'I' is a simple vertical bar.

The image shows a large, stylized logo consisting of the letters 'C', 'C', and 'I' in a bright red color. The letters are set against a solid black background. The 'C's are thick and rounded, and the 'I' is a simple vertical bar. The logo is positioned in the upper left quadrant of the page.

[figure not shown]

[figure not shown]
CCI

The image shows a large, stylized logo consisting of the letters 'C', 'C', and 'I' in a bright red color. The letters are set against a solid black background. The 'C's are thick and rounded, and the 'I' is a simple vertical bar. The logo is positioned in the upper left quadrant of the page.

The image shows a large, stylized logo consisting of the letters 'C', 'C', and 'I' in a bright red color. The letters are set against a solid black rectangular background that covers most of the page. The 'C's are thick and rounded, and the 'I' is a simple vertical bar.

The image shows a large, stylized logo consisting of the letters 'C', 'C', and 'I' in a bright red color. The letters are set against a solid black rectangular background that covers most of the page. The 'C's are thick and rounded, and the 'I' is a simple vertical bar.

CCI

